The study is an open-label clinical trial of orally-administered Trikafta™ in subjects with CF and carrying certain mutations that are without FDA approved modulator treatment. Subjects will be given the study drug elexacaftor 100 mg/tezacaftor 50 mg/ivacaftor 75 mg (2 pills once daily in the morning) and ivacaftor (150 mg) once daily in the evening, as the FDA-registered agent, Trikafta™. Dose and schedule will be identical to what has already been FDA-approved for the F508del CF genotype. Enrollment is planned at two centers, Emory University and University of Alabama at Birmingham. In Substudy 1, patients with residual CFTR function (based on sweat chloride < 80 meq/L or pancreatic sufficiency) will be tested. In Substudy 2, patients with CF encoding the N1303K variant will be enrolled as a “case in point” – emblematic of variants with *in vitro* evidence of Trikafta™ responsiveness who are not approved (i.e., not “on label” for the drug). iPSC-derived airway epithelial monolayers from these patients will be examined for their ability to predict FEV1 and sweat chloride response and other clinical endpoints. Our study will not significantly increase the risks (or decrease the acceptability of risks) associated with the use of Trikafta™ in CF.

Human subject participation will consist of a screening day (-28), day 1 (+/-2), day 7 (+/- 2) [phone call visit], day 14(+/-2), day 28 (+1/- 2) and day 56 (+/-2) follow up (wash-out). The visits will include patient history with concomitant medication review, physical exam, safety laboratory assessments (renal and liver panels, CBC/Diff, urinalysis), serum and urine pregnancy testing, CFTR genotype, spirometry, O2 saturation, sweat chloride test, ophthalmology exam in children, cutaneous punch biopsy and/or blood sample for iPSC derivation, EKG, drug accountability and questionnaire (CFQ-R assessment), and adverse event assessment.

We anticipate the screening and enrollment visit will require 4-6 hours to complete the informed consent, medical history, O2 saturation, concomitant medication review, physical exam, safety laboratory assessments (CBC/Diff, RENAL/LFT chemistry panel, and urinalysis), EKG, CFTR genotyping, questionnaire, serum pregnancy test for females, sweat chloride test, and spirometry.

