#### 11. Statistical Methods For a proposed open-label prospective 4-week trial of Trikafta™.

**Substudy 1:** Patients with CF or CFTR-dependent illness who do not have access to modulator therapy but exhibit a clinical phenotype suggestive of partial/residual CFTR activity.

We will serially evaluate clinical outcomes of interest prior to and after the start of therapy. Change in clinical measurements (spirometry, weight/BMI, quality of life, sweat chloride) will be monitored. Our main goals are to determine the clinical response to Trikafta™ and to determine if *in vitro* responsiveness of iPS cells predicts clinical response. The primary outcome is response to Trikafta™ after 4 weeks of treatment. In this study a clinical response to Trikafta™ at week 4 of treatment will be defined as an improvement, from baseline, in  $FEV_1 > 5\%$  predicted and each subject will be classified a responder or non-responder. In this study, if at least 40% of subjects meet the definition of responder, the drug will be considered efficacious (i.e., comparable to the benefit which led to Orkambi™ approval by FDA following trials in F508del homozygotes). Overall response rate will be accompanied by an approximate binomial 95% confidence interval. To determine the role of iPS *in-vitro* response to Trikafta™, we will compare the  $\Delta Isc$  (change in  $Isc$ ) among Trikafta™ responders and Trikafta™ non-responders using a two-sample t-test or a Wilcoxon rank sum test if distributions are skewed. Additionally, we will correlate the  $\Delta Isc$  obtained from *in vitro* experiments with the change in  $FEV_1\%$  predicted (post minus pre) using Spearman's rank-order correlation with an associated 95% confidence interval. We will also test whether the iPS response reaches a CFTR functional threshold of 40% wild-type levels (a magnitude of activity in primary airway epithelial cells viewed as potentially relevant to clinical benefit). In a sensitivity analysis, we will replicate the  $FEV_1$  analysis with sweat chloride responses, and determine the *in vivo* response rate.

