For other outcomes of interest including sweat chloride levels, quality of life, and weight/BMI, we will apply a mixed effect model to examine the change in these measures over the study duration. Models will include a subject-specific intercept, to account for variability among subjects prior to the start of the treatment, and a categorical variable for time (baseline, day 14, day 28, day 56). A Dunnet's post-hoc comparisons procedure will be used to determine which time points demonstrated a significant change from baseline. Using the same mixed effects models, we will include  $\Delta Isc$  as predictors of *in vivo* improvement. We will also test the interaction between time and  $\Delta Isc$  to determine when *in-vitro* response is most associated with change in clinical response. Adverse events and other safety endpoints will be tabulated and reported using counts and percentages or means and standard deviations, as appropriate.

In addition, because clinical parameters may vary among patients prior to the start of therapy, we will also approach the analysis using a modified N of 1 design configured for the purpose of comparing iPS studies in contrast to the aggregate analysis described above. Using the framework of single subject research, we will evaluate therapeutic response in individual subjects by an interrupted time series (ITS) approach. Briefly, in the absence of an independent control group, ITS analysis is a quasi-experimental design in which each subject acts as their own control and is followed serially in time prior to and after an interruption (in this case, the start of treatment). If the treatment has causal

impact, the post-intervention time series will have a different level or slope than the pre-intervention series. Time series models also have the power to test and correct for possible cyclical patterns and outliers. Using segmented regression analysis, we will conduct ITS models for each of the subjects enrolled in the trial. A significant change in slope from the pre-treatment period will indicate a significant treatment effect. ITS models will be constructed for each outcome of interest where historical and pre-treatment data are available. The change in slope will also be correlated with the *in-vitro* response using Spearman's rank-order correlation coefficient.

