#### Sample size

The FDA has suggested that scientifically meaningful 'binning' of patients based on clinical characteristics can help guide future approval of specific patient groups for drug treatment. The present study is not intended for FDA submission or label expansion of Trikafta™, but as a means to determine whether iPS cells differentiated to respiratory phenotype can be used to predict clinical response to CFTR modulators. For the purposes of this protocol, the subjects enrolled, although potentially of different genotypes, will represent a scientifically meaningful cohort or 'bin' of individuals with partial function mutations, sweat chloride < 80 mmol/L, and/or pancreatic sufficiency. This protocol is designed to compare *in vitro* responsiveness of differentiated iPS cells to *in vivo* clinical activity of Trikafta™, and will test the null hypothesis that the true Trikafta™ response rate of CFTR individuals with partial function mutation genotypes is  $\leq 10\%$  vs. the alternative hypothesis that the true Trikafta™ response rate is  $\geq 40\%$ . We will initially enroll four subjects, and expect all of these individuals will show a clinical response (e.g.,  $> 5\%$  improvement of % predicted FEV1 from baseline). If none of the first four subjects exhibit a response, the study will be terminated. Otherwise, we intend to enroll a total sample size of 22 individuals. Subjects who do not complete the study will be replaced. In this design, if Trikafta™ is ineffective, the probability of early termination after four subjects is 66% and only a 5% chance of concluding the drug is effective (type I error). If Trikafta™ is effective, there is an 86.4% chance of reaching this conclusion. If fewer than four patients show a clinical effect, Trikafta™ will be considered ineffective. To demonstrate the ability of iPS cells to predict clinical benefit, 22 patients will provide at least 80% power to detect a significant correlation of at least  $r = 0.55$  between the changes in clinical outcomes with changes in short circuit current as measured in iPS cells. Tabular details of this analysis are provided below. Power calculations were performed using PASS v. 14 (Kaysville, UT) with a two-sided Z-test and a significance level of 0.05.

	Cumulative # of responses	Decision	95% Confidence Interval (CI)

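### Substudy 1's secondary mixed models name a subject intercept and no other covariance structure, so on-drug standard errors are too small if patients truly differ in response

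*Combined protocol and SAP*

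**What the plan says.** Section 11, Substudy 1, sets the method for the non-FEV1 outcomes: "For other outcomes of interest including sweat chloride levels, quality of life, and weight/BMI, we will apply a mixed effect model". Its only variance component is described as follows: "Models will include a subject-specific intercept, to account for variability among subjects prior to the start of the treatment". Time enters as "a categorical variable for time (baseline, day 14, day 28, day 56"). A Dunnett "post-hoc comparisons procedure will be used to determine which time points demonstrated a significant change from baseline". ΔIsc is then added to the same models, and the plan continues: "We will also test the interaction between time and" ΔIsc, in order to learn when the in vitro response matters most. For these models the section gives no random treatment or time effect, no residual covariance, no robust standard error and no degrees-of-freedom method.

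Three other statements bear on this:
- For FEV1, "each subject will be classified a responder or non-responder".
- In the sample size text, "we intend to enroll a total sample size of 22 individuals". They may have different genotypes, and power is given for a correlation of 0.55 between clinical change and change in short circuit current.
- The last visit is the "day 56 (+/-2) follow up (wash-out"), about four weeks after the last dose.

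**The concern.** A random intercept with categorical time implies compound symmetry. Patients may start at different levels, but beyond visit-to-visit noise they all change by the same amount, so Day 14, Day 28 and Day 56 changes share one variance. The trial's premise is that response varies between patients and that ΔIsc explains part of that variation.

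If responses vary, on-drug changes are more dispersed than off-drug ones. The model averages them into one residual on (22 − 1) × (4 − 1) = 63 degrees of freedom, where a single between-patient change has 22 − 1 = 21.

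Two results are at stake: the precision claimed for on-drug improvement in the secondary outcomes, and the time-by-ΔIsc contrasts. The contrasts matter more, because iPS prediction is one of the study's main goals.

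**Working it through.** **The plan's own figures.** No standard error or power is given for these models. The nearest figures are in the Substudy 2 sample size text: n = 20, one-sided α 0.025, sweat chloride. Noncentral-t power is 99.2% (difference 10, SD 9.7), 80.7% (10, SD 15) and 98.9% (15, SD 15), against the stated 99%, 81% and 98.9%. The chance rate is P(Z < −15/9.7) = 6.1%, against the stated 6%. These reproduce, so both SDs are used in the illustration below.

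**Set-up.** Let s² be the visit noise variance, τ² the between-patient variance of true response, and c the share of each patient's response still present at Day 56. The response pattern over the four visits is u = (0, 1, 1, c).

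- Expected residual mean square of the random-intercept fit: s² + τ²[u'u − (1'u)²/4]/3.
- Model variance of any change, per patient: 2s² + kτ², where k = 2/3 − 2c/3 + c²/2.
- True variance: 2s² + τ² on drug; 2s² + c²τ² at Day 56.

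Let f = τ²/(2s² + τ²), the share of on-drug change variance that is true response. On drug, model variance / true variance = 1 − (1 − k)f:
- c = 0: k = 2/3, ratio 1 − f/3. The SE ratio is 0.96, 0.91 and 0.87 for f = 0.25, 0.50 and 0.75.
- c = 0.5: k = 0.4583, ratio 1 − 0.5417f. The SE ratio is 0.93, 0.85 and 0.77.

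**Where the Day 56 direction changes.** Setting k = c² gives 3c² + 4c − 4 = 0, so c = 2/3. Below that the Day 56 standard error is too large; above it, too small.

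**Error rates.** Simulation with n = 22, four visits, balanced data, 20,000 to 40,000 trials per run. Separate runs agree to about half a percentage point.

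| Nominal 5% | f = 0.25 | f = 0.50 | f = 0.75 |
|---|---|---|---|
| Day 28 interval misses, c = 0 | 6.2% | 7.4% | 9.2% |
| Day 28 interval misses, c = 0.5 | 6.6% | 9.4% | 13.2% |
| Day 28 ΔIsc slope contrast, c = 0 | 6.1% | 7.3% | 9.2% |
| Any false Dunnett rejection, c = 0 | 5.1% | 5.6% | 6.2% |
| Any false Dunnett rejection, c = 0.5 | 6.3% | 7.8% | 10.4% |
| Day 56 interval misses, c = 0 | 3.2% | 1.4% | 0.1% |
| Day 56 interval misses, c = 0.5 | 4.3% | 3.6% | 2.6% |
| Day 56 interval misses, c = 1 | 6.5% | 8.8% | 12.0% |

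At c = 0.5 the slope contrast reaches about 13%. At f = 0 all rates are about 5%. A paired t-test on the same data holds 4.9% to 5.1%.

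**Illustration in mmol/L.** Assume that 9.7 is the noise-only SD of change and 15 the total on-drug SD. Then τ² = 225 − 94.09 = 130.91 (τ = 11.4) and f = 130.91/225 = 0.58. With c = 0 and n = 22:
- Model SE at every visit: √[(94.09 + 130.91 × 2/3)/22] = 2.87.
- True SE on drug: √(225/22) = 3.20, so the model is 10% too small.
- True SE at Day 56: √(94.09/22) = 2.07, so the model is 39% too large.
- On-drug slope contrasts: simulated model SE 3.03 against true 3.44, with false-positive rate 8.0% to 8.2%. The joint 3-df interaction test rejects 7.2%.

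With total SD from 12 to 20 and noise SD 9.7, the on-drug SE ratio runs from 0.94 to 0.86. With full wash-out it cannot fall below √(2/3) = 0.82.

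**The case against.** Several points on the other side stand.

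- The text says what the models include. It does not say that nothing else may be added. A reader might infer that richer structures are ruled out, and the documents do not support that. What they support is that the intercept is the only structure prespecified, and a programmer following the text would fit it.
- A reader might take the per-visit rates as the error of the planned Dunnett procedure. They are not: with full wash-out its family-wise error stays at 5% to 6.5%.
- For the mean change, excess rejection needs a zero average effect together with real individual responses that cancel out. If the drug does nothing in anyone, f = 0 and error is nominal. What remains for the mean is under-coverage when the drug works. The interaction contrasts need no such unusual null, only response differences unrelated to ΔIsc.
- The interaction model does let response vary with ΔIsc. It excludes only differences among patients with the same ΔIsc. At r = 0.55, ΔIsc explains 0.55² = 30% of change variance, which leaves room for such differences.
- It is tempting to say that Day 56 intervals are always too wide. The documents give no wash-out course for quality of life or weight/BMI, so the direction can go either way.
- The FEV1 responder rule, the ΔIsc comparison between responders and non-responders, the Spearman correlations and the single-subject time series do not use this model.
- Extending the point to Substudy 2 is not supported. Its mixed models name no random intercept and stop at day 28.

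**Conclusion.** The concern holds for Substudy 1's secondary mixed models. On the plan's premise that patients differ in response, on-drug standard errors and on-drug time-by-ΔIsc contrasts are too small. The size is moderate: for f from 0.25 to 0.75, Day 28 misses of about 6% to 9% with full wash-out and 7% to 13% with half the response persisting, against a nominal 5%. The slope contrast behaves similarly.

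The Day 56 error is too wide or too narrow depending on whether more than about a third of the individual response has gone. Both f and c are assumptions. Splitting the two Substudy 2 SDs into noise and response is also an assumption, and it applies to sweat chloride only. The primary conclusion is not at risk. The change is worth making because the interaction test bears directly on iPS prediction.

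**What to change.** In section 11, Substudy 1, replace the intercept sentence with an unstructured covariance over baseline, Day 14, Day 28 and Day 56, with Kenward-Roger degrees of freedom. State that it applies to both the change-from-baseline and the time-by-ΔIsc models. Name a fallback in case it does not converge, for example a heterogeneous structure, or the random intercept with empirical standard errors and a small-sample correction.

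The cost is one sentence and one SAS statement, and no new data. The unstructured form has 4 × 5/2 = 10 covariance parameters. On-drug intervals become somewhat wider: in the illustration the SE goes from 2.87 to 3.20, which is the correction itself, and the lower degrees of freedom add a little. No change to the Substudy 2 mixed models is shown to be needed.

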As part of an evaluation to test the relationship between CFTR activity and modulator effectiveness, we worked with 43 rare CFTR variants stably expressed from a single site in the genome of the human CF bronchial epithelia cell line (CFBE41o-) (Han et al., 2018). The magnitude of drug response in these cell models was highly correlated with residual CFTR function for the potentiator ivacaftor, the corrector lumacaftor, and ivacaftor-lumacaftor combination therapy. Response of a second set of 16 variants expressed stably in FRT cells showed similar correlation (although certain variants were identified that demonstrate significantly higher response to modulator treatment than predicted by *in vitro* analysis). In addition, nearly all variants studied in CFBE (40/43) and FRT cells (13/16) demonstrated greater response to ivacaftor-lumacaftor combination therapy than either drug alone. Together, the variants studied here represent 87% of individuals in the CFTR2 database with at least one missense defect. Our results therefore indicate that most patients with CF carrying missense variants are likely to: 1) respond modestly to current potentiator and/or corrector therapy, while a small fraction will exhibit more pronounced CFTR rescue and 2) derive the greatest benefit from combination treatment.

**Overview** FDA has indicated new *in vitro* model systems capable of predicting *in vivo* clinical benefit may represent a significant and unmet need for advancing personalized CF therapeutics. The present study is designed to specifically and prospectively test iPS cells taken from patients encoding rare CF variants as a means to determine *in vitro* thresholds for CFTR rescue. Using iPS cells differentiated to exhibit a respiratory epithelial phenotype, we will determine whether the cells can be used to predict FEV1 response among individuals carrying rare, partial function mutations who receive

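### In Substudy 1's mixed models for sweat chloride, quality of life and weight/BMI, the ΔIsc main effect is called a predictor of improvement but measures association with outcome level, not with change

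*Combined protocol and SAP*

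**What the plan says.** All of this is in Section 11, Statistical Methods, under Substudy 1.

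- Scope: "For other outcomes of interest including sweat chloride levels, quality of life, and weight/BMI, we will apply a mixed effect model".
- Structure: "Models will include a subject-specific intercept, to account for variability among subjects prior to the start of the treatment", together with "a categorical variable for time (baseline, day 14, day 28, day 56"). Baseline is therefore one of the modelled responses, and the response is the outcome level at each visit.
- In vitro predictor: "Using the same mixed effects models, we will include" ΔIsc "as predictors of *in vivo* improvement".
- Interaction: "We will also test the interaction between time and" ΔIsc. Its stated purpose is to find the time at which the in vitro "response is most associated with change in clinical response".

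The paragraph does not say that the interaction is the test of prediction, that baseline becomes a covariate, or that the response becomes change from baseline. The significance level for all analyses is 0.05. Section 5 describes Day 56 as the wash-out visit.

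For FEV1, the same section does analyse change. It compares ΔIsc between responders and non-responders, and takes a Spearman correlation of ΔIsc with the post-minus-pre difference in percent predicted.

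**The concern.** A subject can have a low sweat chloride at every visit, including before the first dose, and not improve at all. If such subjects also have large ΔIsc, the main effect is significant and, as the paragraph is worded, would be read as in vitro response predicting clinical improvement.

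The protocol gives a reason to take this seriously. The Introduction reports earlier work on variants expressed in cell lines: "The magnitude of drug response in these cell models was highly correlated with residual CFTR function". Section 5 uses sweat chloride below 80 meq/L as one marker of residual function for this same substudy. Larger ΔIsc could then go with lower sweat chloride before any drug is given. That is the same direction as benefit, so the artefact would look like support.

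The main effect can also miss a real link, because it averages two on-drug visits with an untreated baseline and a wash-out visit.

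**Working it through.** **1. Nearest stated figure.** The plan gives no power or error rate for this mixed-model test. The closest is at least 80% power for r = 0.55 between changes, n = 22, two-sided 0.05. Fisher z: Φ(atanh(0.55)·√19 − 1.96) = Φ(0.618 × 4.359 − 1.96) = Φ(0.735) = 76.9%. With the bias term r/(2(n−1)) it is 78.6%. This roughly reproduces the figure, and the point below does not depend on it.

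**2. What the coefficients estimate.** Let β0, β14, β28 and β56 be the slopes of the outcome on ΔIsc at each visit.

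- Main effect, no interaction, complete data: (β0 + β14 + β28 + β56)/4. The test is the regression of each subject's four-visit mean on ΔIsc, with 20 df.
- ΔIsc coefficient with the interaction in the model and baseline as reference: β0.
- Interaction at Day 28: β28 − β0. Only this one is about change.

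If ΔIsc tracks level only, all four slopes equal β0; the main effect estimates β0 and the contrast estimates 0. If ΔIsc predicts a change δ at Days 14 and 28 only, the main effect estimates δ/2 and the contrast estimates δ. A random intercept does not adjust for baseline, so it does not alter this.

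**3. Rejection with no link to change.** Assumed, not in the documents: between-subject SD 15, within-subject SD 7, and correlation ρ between ΔIsc and the subject's underlying level. The correlation of ΔIsc with the four-visit mean is ρ × 15/√(225 + 49/4) = 0.974ρ. Rejection is about Φ(√19·atanh(0.974ρ) − 1.96), plus the opposite tail.

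| ρ | Correlation with mean | Formula | Simulated main effect | Simulated Day 28 contrast |
|---|---|---|---|---|
| 0 | 0 | 5% | 5% | 5% |
| 0.1 | 0.097 | 7% | 7% | 5% |
| 0.2 | 0.195 | 14% | 13–14% | 5% |
| 0.3 | 0.292 | 26% | 26–27% | 5% |
| 0.5 | 0.487 | 64% | 66% | 5% |
| 0.7 | 0.682 | 95% | 96% | 5% |

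The result does not depend closely on the SDs. With intraclass correlation from 0.5 to 0.9, the main effect at ρ = 0.5 rejects in 57–67% of trials. The baseline-reference coefficient rejects in 37–63%.

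**4. Power with a real link.** Assumed: true change of SD 10, correlation 0.7 with ΔIsc (slope 7 per SD of ΔIsc), full effect at Days 14 and 28, none at Day 56, ρ = 0, within-subject SD 7.

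- Main effect: the slope on the mean is 7/2 = 3.5, and the variance of the mean is σb² + 49/4 + 100/4. For σb = 15, r = 3.5/√262.25 = 0.216, power 16%. For σb = 10, r = 3.5/√137.25 = 0.299, power 27%. For σb = 7, r = 3.5/√86.25 = 0.377, power 41% by formula and 42% simulated.
- Day 28 contrast: r = 7/√(100 + 2 × 49) = 0.497, power 66% by formula and 68% simulated, whatever σb is.

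With r = 0.55 between ΔIsc and Day 28 change and ρ = 0, the main effect has 10–44% power over intraclass correlations 0.9 to 0.5, and the contrast 81%. If ρ is −0.3 relative to the direction of the effect, main-effect power falls to 5–10%, so correlation of opposite sign can hide a real link.

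**The case against.** The best defence is that the right test is already there. The sentence after the ΔIsc main effect plans the interaction and ties it to change, the paragraph opens by saying that the models examine change, and an interaction normally brings its main effect with it. The two sentences could describe one model. This stands in part: the needed term is planned. But the label of predicting improvement is attached to ΔIsc itself, and the interaction is assigned only to timing. If both are fitted together, the ΔIsc coefficient is the baseline association, which is no nearer to improvement.

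A second defence is that the correlation with level is unknown. This stands. The supporting statement comes from cell lines expressing single variants, tested with ivacaftor and lumacaftor. It does not concern patient-derived iPS monolayers treated with Trikafta, and the link to quality of life or weight is more remote than to sweat chloride. At ρ = 0 the main effect holds 5%.

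A reader might infer that a spurious main effect would confirm the trial's central hypothesis. The documents do not support that. The hypothesis is about FEV1 and is tested on change. Section 11 also repeats the FEV1 analysis with sweat chloride responses as a sensitivity analysis, and correlates each subject's change in slope with in vitro response where pre-treatment data exist. A misleading main effect would appear beside these results. Nor do the documents support the reading that the plan lacks any test of change for these outcomes.

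The false-positive rates and the 16–42% power belong to different scenarios (ρ above zero and ρ equal to zero) and should not be quoted as occurring together.

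**Conclusion.** Wrong as written, with limited reach. For sweat chloride, quality of life and weight/BMI in Substudy 1, the term that the plan calls a predictor of improvement estimates association with level. That follows from the model's form and needs no assumed numbers.

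The size of the harm does rest on assumptions. With SDs of 15 and 7, false rejection runs from 5% at ρ = 0 to about 66% at ρ = 0.5, against 5% for the Day 28 contrast. With a real link and ρ = 0, main-effect power is about 16–42% for between-subject SD 15 to 7, against 68%. The calculations assume complete data at all four visits.

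The primary FEV1 analyses are not affected, and no stated sample size, power figure or decision rule depends on this point.

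**What to change.** Add to the mixed-model paragraph of Section 11, Substudy 1, that:

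- the test of iPS prediction in these models is the ΔIsc by time contrast at Day 28 versus baseline, with the Day 14 contrast as supportive; and
- the ΔIsc main effect is kept in the model but is not interpreted as prediction of improvement.

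The cost is one or two sentences. The model and the data stay the same, and no visits or subjects are added.

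### The per-subject time-series analysis scores change in slope alone, so a benefit held from Day 14 to Day 28 can score zero, or reversed if a faded Day 56 is included

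*Combined protocol and SAP*

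**What the plan says.** Section 11, Substudy 1, adds a modified N-of-1 analysis, "configured for the purpose of comparing iPS studies in contrast to the aggregate analysis described above". Each subject "is followed serially in time prior to and after an interruption (in this case, the start of treatment"), and segmented regression is fitted subject by subject. If treatment works, the plan says, "the post-intervention time series will have a different level or slope than the pre-intervention series".

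The scoring rule that follows drops level: "A significant change in slope from the pre-treatment period will indicate a significant treatment effect". The link to the laboratory data also uses slope only: "The change in slope will also be correlated with the" in-vitro response, by Spearman's coefficient. On the data to be used, the plan says only that "ITS models will be constructed for each outcome of interest where historical and pre-treatment data are available".

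No regression equation is given, and the start of treatment is the only break named. Section 5 lists the clinic visits after the start as "day 14(+/-2), day 28 (+1/- 2) and day 56 (+/-2) follow up (wash-out"), with a 28-day drug supply, so only Days 14 and 28 are on drug. The mixed model in the same part of Section 11 gives Day 56 its own category: "a categorical variable for time (baseline, day 14, day 28, day 56"). The ITS text has no equivalent rule, and it states no direction of benefit per outcome.

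**The concern.** With two on-drug visits, slope measures mainly what happens between Day 14 and Day 28. A subject who improves by Day 14 and stays improved has a change in level and no change in slope. Such a subject meets the plan's own idea of response, which is a change from baseline at week 4, yet the ITS would record no effect. If the wash-out visit is treated as one more point after the start of treatment, loss of benefit off drug pulls the fitted slope down, and the best responders get the most adverse scores.

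This analysis exists to set individual response against iPS response. A null or negative ITS correlation could be misread as failure of the iPS assay. A positive one would carry little weight if the model had been chosen after the data were seen.

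**Working it through.** The plan gives no power or error rate for the ITS, so there is no figure to reproduce.

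**Inputs from the documents.** Visits at screening, Day 1, Day 14, Day 28 and Day 56 (wash-out); significance level 0.05; 22 subjects.

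**Assumed inputs.** Six pre-treatment points ending at Days -28 and 1, in three spacings (first point at Day -140, -148 or -393); a 10-point effect; independent noise with SD 3, 4 or 5. For Spearman: response mean 5 and SD 5, and correlation 0.7 with iPS response. The documents do not give the time course between Days 14 and 28, or the loss of effect after Day 28.

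**Level-plus-slope model.** y = a + b1·t + b2·post + b3·post·(t - 1). The slope change b3 is the post-start slope minus the pre-treatment slope. Measure all values against the pre-treatment trend.

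- *Days 14 and 28 only, benefit b at both:* b3 = (b - b)/(28 - 14) = 0 for any b.
- *Day 56 added, share f of the benefit kept:* the mean of 14, 28 and 56 is 32.67, and the sum of squares is 18.67² + 4.67² + 23.33² = 914.67. Then b3 = [(-18.67 - 4.67)b + 23.33·f·b]/914.67 = -0.0255·b·(1 - f) per day. With b = 10 and f = 0, b3 = -0.255.

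Simulation used 100,000 subjects per cell for the tests and 3,000 trials of 22 subjects for Spearman. Ranges span the spacings and SDs.

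| Held step, level-plus-slope | Slope change per day | Subjects significant | Mean Spearman |
|---|---|---|---|
| Day 56 excluded | 0 | 2.5% positive (chance) | 0.00 |
| Included, 0% kept | -0.255 | 22-48% negative | -0.38 to -0.52 |
| Included, 25% kept | -0.191 | 14-32% negative | -0.31 to -0.45 |
| Included, 50% kept | -0.128 | 9-17% negative | -0.23 to -0.35 |
| Included, 75% kept | -0.064 | 5-8% negative | -0.11 to -0.19 |
| Included, 100% kept | 0 | 2.5% (chance) | 0.00 |

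**Same model, effect still rising (5 at Day 14, 10 at Day 28).** Without Day 56, b3 = 5/14 = +0.357 per day, 8-15% of subjects are significantly positive, and Spearman is +0.21 to +0.33. With Day 56, b3 is:

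- effect gone: (-18.67·5 - 4.67·10)/914.67 = -0.153 (Spearman -0.26 to -0.39);
- half kept: -0.026;
- fully kept: +0.102 (Spearman +0.18 to +0.30).

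**No level term, held step.** Without Day 56, 21-52% are significantly positive and Spearman is +0.40 to +0.54. With Day 56, Spearman is -0.13 to +0.04 if the effect has gone and +0.32 to +0.52 if fully kept.

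**On-drug indicator for Days 14 and 28, pre-treatment trend kept, Day 56 excluded or given its own term.** The step is estimated at 10.0 whatever remains at Day 56; 31-77% are significant and Spearman is +0.43 to +0.56. For the rise it estimates the on-drug average, 7.3-7.4, with 17-43% significant and Spearman +0.35 to +0.51.

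**Two further checks.** Adding a level term is not enough without a Day 56 rule: for a true 5-point benefit, the level estimate becomes 6.19 if half has faded by Day 56 and 7.37 if all has. With only screening and Day 1 before treatment, the level-plus-slope fit has four parameters for four points (no residual degrees of freedom), or for five points if Day 56 is added.

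**The case against.** The strongest reply is that the level-or-slope sentence describes ITS in general, and that a plan scoring slope alone may intend joined segments with no level term. On that reading, with Day 56 left out, slope does pick up a step, and its correlation with iPS response (+0.40 to +0.54) is close to that of the proposed measure (+0.43 to +0.56). This is right, but the plan does not state that model, and the model fails if a faded Day 56 enters.

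The negative result also needs benefit to have been lost by Day 56, which is a fact about patients and not a choice in the plan. That condition stands; with a fully kept step the results are null or positive only.

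The 10-point effect is generous, being twice the plan's responder threshold. With a 5-point step, wrong-direction significance under full fade falls to 9-17%. The on-drug indicator then detects 11-28% of subjects, against 9-21% for slope without a level term or Day 56. Every per-subject test is then weak, but the zero and reversed correlations remain.

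For FEV1, scoring level largely repeats the planned correlation of Isc change with FEV1 change (Day 28 minus Day 1 gives +0.37 to +0.50 here), apart from adjusting for the pre-treatment trend. The analysis is also supplementary, with no decision attached. Both points limit the consequence. They do not make the scoring rule sound.

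**Conclusion.** The concern holds. The plan says an effect may be a change in level or slope, then scores slope only, and leaves the level term and Day 56 unspecified; this needs no assumption. In a level-plus-slope fit with Day 1 before the break, a benefit constant against the subject's pre-treatment trend scores exactly zero. The score reverses if Day 56 is in the post-start segment and the benefit has at least partly faded. If values are merely flat after a decline of 2 points per year, the slope change is +2 points per year whether the benefit is 0, 5 or 10, so it still says nothing about the benefit. Placing Day 1 after the break would give a positive slope instead (+0.18 per day for a 5-point benefit).

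Given some fade, the ITS correlation with iPS response can come out positive, null or negative on one dataset, depending on choices the plan does not state. The rates rest on the assumed effect shapes, noise and number of historical points. The effect is confined to this supplementary Substudy 1 analysis. The responder rule, the Isc-FEV1 correlation, and the mixed model with its time-by-Isc interaction are untouched.

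**What to change.** Amend the ITS text in Section 11 as follows.

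- State the regression model.
- Make the on-drug level change (one indicator for Days 14 and 28, with the pre-treatment trend kept where historical data allow) both the ITS effect measure and the quantity correlated with Isc change. A single indicator is preferable to the level term of the full level-plus-slope model, which without Day 56 reaches significance in only 10-21% of subjects.
- Exclude Day 56 or give it its own term; the on-drug estimate is the same either way. Do not code Day 56 as off-drug, which assumes complete wash-out: a 10-point step would then be estimated at 7.9-8.3 if half is kept and 5.7-6.6 if all is kept.
- State the direction of benefit for each outcome (a rise in FEV1, a fall in sweat chloride).
- Report slope change descriptively, and present the per-subject tests as supportive, since two on-drug points leave any of them weak.

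The change is wording only and uses the same data. It has three costs. Slope is no longer a formal criterion for slowly changing outcomes such as weight/BMI. An effect still rising at Day 28 would be detected somewhat less often than by a slope-only model without Day 56 (17-43% against 23-60%). If wash-out is in fact complete, not using Day 56 as off-drug data costs some power (31-77% against 45-87%).
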